6.2. Concomitant Therapy

1. Concomitant Therapy :

1.1 TEGAFOX(one cycle):

*Oxaliplatin (own expense) 85 mg/m² in D5W 250 ml IVF 2 hrs, D1, every 2 wks

*Tegafur-uracil 300mg/m²/day and leucovorin 90mg/day, given on days 1 to 5 and 8 to 12 days, every 2 weeks

1.2 FOLFOX(one cycle):

*Oxaliplatin (own expense) 85 mg/m² in D5W 250 ml IVF 2 hours, D1

*Calcium Folinate 100 - 400 mg/m² in D5W 250ml IVF 2 hours, D1

*5-FU 400 mg/m² IV bolus on D1 *5-FU (2400 mg/m²) IVF 46 hrs, Repeat every 2 weeks
1.3 UFUR (one cycle)

*Tegafur 300-350 mg/m²/day and leucovorin 90mg/day PO on day 1 to day 5, then rest for 2 days for 2 weeks

1.4 The radiation therapy modules are as follows:

Short-Course (hypofractionated, 25 Gy/5 fractions) Radiotherapy (SCRT)

2. Prohibited Therapy : cell therapy, immunotherapy

7. Efficacy Assessments

1. **Grade 3 enteritis/proctitis**: evaluated by National Cancer Institute Common Terminology Criteria for Adverse Events Version 5.0 (NCI CTCAE v. 5.0) and the criteria of the Radiation Therapy Oncology Group (RTOG) and European Organization for Research and Treatment of Cancer (EORTC). The sign or symptoms of radiation proctitis (diarrhea, rectal bleeding, rectal pain) is evaluated and recorded by our research nurse 2 to 4 weeks after radiation therapy completed. Colonoscopy evaluation for Vienna Rectoscopy Score will take place 2 to 3 weeks after the radiation therapy is completed.
2. Any grade III adverse events during the neoadjuvant therapy: evaluated by clinicians according to National Cancer Institute Common Terminology Criteria for Adverse Events Version 5.0 (NCI CTCAE v. 5.0) every cycles of chemotherapy. An additional evaluation and record will be recorded by the research nurse every 3 cycles of chemotherapy.
3. Clinical complete response rate of the primary tumor after completion of the neoadjuvant treatment: evaluated by Response Evaluation Criteria in Solid Tumors Version 1.1 (RECIST v1.1) after neoadjuvant chemotherapy and radiation therapy completed
4. Pathological or clinical complete response rate of the primary tumor after completion of the neoadjuvant treatment: defined as no residual cancer cells in the resected specimen after curative resection
5. Patient's tolerability and completion rate of the neoadjuvant therapy

8. Safety Assessments

The complete blood count is evaluated on each admission for chemotherapy. The adverse events is evaluated according to National Cancer Institute Common Terminology Criteria for Adverse Events Version 5.0 (NCI CTCAE v. 5.0). Serum creatinine, electrolyte, AST, ALT, total and direct bilirubin is examined on each 3 cycle of chemotherapy.

If ALT or AST exceeds three times the upper limit of normal (3×ULN), curcumin administration will be suspended. This 3×ULN threshold is a commonly used warning indicator for drug-induced liver injury. In such cases, we will monitor liver function tests weekly until the values recover to <1.5×ULN or return to baseline.

9. Adverse event reporting

[name] will report SAEs to the IRB of Chang Gung Medical Foundation according to the Serious Adverse Event Reporting Procedures and Guidelines as posted in the Clinical Trials Resource on the website of Chang Gung Medical Foundation IRB. SAE reports to the IRB should include the following information when calling the Medical Monitor:

- Date and time of the SAE
- Date and time of the SAE report
- Name of reporter
- Call back phone number
- Affiliation/Institution conducting the study
- Protocol number
- Title of protocol
- Description of the SAE, including attribution to drug and expectedness

9.1 Definitions and reports of Adverse Events

All adverse events that occur after the informed consent is signed (including run-in) must be recorded on the adverse event CRF (paper and/or electronic) whether or not related to study agent. AE Data Elements including:

- AE reported date
- AE Verbatim Term
- CTCAE Term (v 5.0)
- Event onset date and event ended date
- Severity grade
- Attribution to study agent (relatedness)
- Whether or not the event was reported as a Serious Adverse Event (SAE)
- Action taken with the study agent
- Outcome of the event
- Comments

Identify the adverse event using the NCI Common Terminology Criteria for Adverse Events (CTCAE) version 5.0. The CTCAE provides descriptive terminology and a grading scale for each adverse event listed.

AEs will be assessed according to the CTCAE grade associated with the AE term. AEs that do not have a corresponding CTCAE term will be assessed according to their impact on the participant's ability to perform daily activities as follows:

Grade	Severity	Description
1	Mild	
• Barely noticeable, does not influence functioning• Causing no limitations of usual activities
2	Moderate	
• Makes participant uncomfortable, influences functioning• Causing some limitations of usual activities
3	Severe	
• Severe discomfort, treatment needed• Severe and undesirable, causing inability to carry out usual activities
4	Life threatening	
• Immediate risk of death• Life threatening or disabling

5	Fatal	• Causes death of the participant
---	-------	-----------------------------------

The possibility that the adverse event is related to study drug will be classified as one of the following: not related, unlikely, possible, probable, definite.

DEFINITION of Serious Adverse Events: ICH Guideline E2A and GCP of Taiwan define serious adverse events as those events, occurring at any dose, which meet any of the following criteria:

- Results in death
- Is life threatening (Note: the term life-threatening refers to an event in which the patient was at risk of death at the time of the event; it does not refer to an event which hypothetically might have caused death if it were more severe).
- Requires inpatient hospitalization or prolongation of existing hospitalization
- Results in persistent or significant disability/incapacity
- Is a congenital abnormality/birth defect
- Events that may not meet these criteria, but which the investigator finds very unusual and/or potentially serious, will also be reported in the same manner.

9.2 Adverse event follow-up

All AEs, including lab abnormalities that in the opinion of the investigator are clinically significant, will be followed according to good medical practices and documented as such. Site staff should send follow-up reports as requested when additional information is available. Additional information should be entered on the IRB of Chang Gung Medical Foundation of SAE form in the appropriate format. Follow-up information should be sent to Chang Gung Medical Foundation IRB as soon as possible according to IRB's Serious Adverse Event Reporting Procedures and Guidelines.

10. Criteria for the termination of the trial

1. The drug's lack of efficacy is proven early for failure to obtain the expected benefit. Treatment does not lead to an equal or better result than the treatment against which is compared.
2. Be shown prematurely that the drug is harmful, resulting in a risk for patients enrolled in the trial.
3. Logistics issues for being unable to recruit the expected number of subjects. It is important to publish this type of trial indicating problems observed and the causes leading to early termination since they can help other investigators avoid the same problems and repeating the same mistakes.

11. Statistical Considerations

Quantitative variables will be presented as mean±standard deviation (SD) and categorical variables will be presented as proportions. The Student t-test, Mann-Whitney U-test and Spearman rank correlation test will be used to analyze differences between groups of variables.

11.1 Sample size Determination

Sample size calculation is performed using one proportion equality test using the exact test to achieving an 80% power at the 5% level of significance. With the expectation of an -15%

of improvement of acute radiation proctitis (30% to 15%), the total estimated patients number in a single-arm trial required is 64. Consider the patient with incomplete data and drop-out rate of 10%, the total estimated number of sample size is 72. Sample size calculation was performed using PASS software (Power Analysis and Sample Size version 2021, NCSS, Kaysville, Utah, USA).

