This study aims to investigate the anti-inflammatory and anti-cancer properties of high-bioavailability curcumin in patients with mid-to-low rectal cancer undergoing neoadjuvant chemoradiotherapy. Curcumin is generally considered to have a high safety profile, and its oral formulation has been classified by the U.S. Food and Drug Administration (FDA) as “**Generally Recognized as Safe**” (GRAS) (GRAS Notice [GRN] No. 686). Reports of adverse effects related to curcumin are rare and primarily involve interference with bile secretion and iron metabolism.[1, 2] However, despite numerous molecular studies demonstrating curcumin’s anti-cancer and anti-inflammatory mechanisms, as well as its excellent oral safety, its oral bioavailability remains extremely low due to its lipophilic nature. Previous human studies have shown that even with oral administration of 12 grams of curcumin, the serum concentration only reaches 0.051 mg/mL[3], and approximately 75% of orally administered curcumin is excreted via feces.[4] The primary objective is to evaluate whether curcumin can reduce radiotherapy-associated adverse effects, such as radiation-induced enteritis, and improve the pathological complete response (pCR) rate to chemoradiotherapy. In addition, translational research will be conducted on tumor tissue samples collected at different time points to elucidate the underlying molecular mechanisms.

Investigational product(s) :

High-Bioavailability Curcumin (BCM95 curcumin)

Development Phase : I II III IV 其它 _____ 不適用

Study Design :

1. Experimental Group

Control Group : Placebo
 Study Drug (Name、Dose、Usage) _____
 Other _____

2. Blinding : Open Evaluator-blind Single-blind(patient) Double-blind(patient+PI)
 Double Dummy Other _____

3. Randomization: Yes No

4. Parallel design Crossover design Other single arm Not applicable

5. Treatment Period : 5 months Not applicable

6. Study Period: 3 years (or From 2026/01/01 to 2029/12/31)

6. Dose adjustment : Mandatory Selectively No Not applicable

7. Study location : Single Multi-center Global

Endpoints (Outcome measure) :

1. Primary endpoint:

1. **Grade 3 enteritis/proctitis** or grade 3 GI AE: evaluated by National Cancer Institute Common

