1.3 UFUR (one cycle)

*Tegafur 300-350 mg/m²/day and leucovorin 90mg/day PO on day 1 to day 5, then rest for 2 days for 2 weeks

1.4 The radiation therapy modules are as follows:

Short-Course (hypofractionated, 25 Gy/5 fractions) Radiotherapy (SCRT)

2. Prohibited Therapy : cell therapy, immunotherapy

Statistical Methods :

1. Main study Hypothesis : Equality Superiority Non-inferiority
 Equivalence Other

2. Estimated Sample Size : 整個試驗預計納入人數_72_，整個試驗可評估人數_64_
 本中心預計納入人數_72_，本中心可評估人數_64_

3. Efficacy assessment group : Intent-to-treat (ITT) Per-Protocol (PP)
 Other _____

附註：意圖治療：Intent-to-treat (ITT)；依計畫書：Per-Protocol (PP)

4. Interim analysis : Yes No

5. Statistical methods : descriptive statistics, Kaplan-Meier method, T-test

6. Handling of Missing Data : Listwise deletion

2. Introduction and Rationale

The primary treatment method for non-metastatic locally advanced rectal cancer is TME (Total mesorectal excision). In recent years, neoadjuvant chemotherapy and radiation therapy have been proven to decrease local recurrence and increase the possibility of organ preservation. [5, 6] However, radiation proctitis is a joint adverse event in one-third of patients one week after radiation treatment is complete; [7] and severe acute toxicity was observed in 4.2% of patients. [8]

Curcumin (diferuloylmethane) is a hydrophobic polyphenol derived from the rhizome of *Curcuma longa*. It has been proven an anti-inflammatory agent as an NF- κ B inhibitor [9] and has numerous intrinsic and extrinsic anti-neoplastic pathways. [10] The murine model showed that oral curcumin could alleviate irinotecan-induced intestinal injury via attenuation of NF- κ B activation, oxidative stress and endoplasmic reticulum stress. [11] One phase I clinical trial showed the oral form curcumin can be safe even up to 8 gram per day. [12] Moreover, the USFDA has designated oral curcumin as a “generally recognized as safe” agent. (US FDA; per 21 CFR 182.10, 182.20) However, due to its hydrophobic feature, poor bioavailability limited its clinical application. [13]

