2.5 Regulatory

This study will be conducted in compliance with the protocol approved by the Institutional Review Board, and according to Good Clinical Practice standards. No deviation from the protocol will be implemented without the prior review and approval of the IRB except where it may be necessary to eliminate an immediate hazard to a research subject. In such case, the deviation will be reported to the IRB as soon as possible.

3. Objectives and Endpoints

3.1 Study Objectives:

3.1.1 *Primary objective*: the anti-inflammation effect of curcumin on the radiation proctitis, adverse events and completion of neoadjuvant radiation therapy and chemotherapy

3.1.2 *Secondary objectives*: the anti-neoplastic effect of curcumin on the treatment of rectal cancer in adjuvant with radiation therapy and chemotherapy

3.2 Study endpoints:

3.2.1 *Primary endpoint*:

1. **Grade 3 enteritis/proctitis**: evaluated by National Cancer Institute Common Terminology Criteria for Adverse Events Version 5.0 (NCI CTCAE v. 5.0) and colonoscopy evaluation 2 weeks after radiation therapy completed

3.2.2 *Secondary endpoints*:

1. Any grade III adverse events during the neoadjuvant therapy: evaluated by National Cancer Institute Common Terminology Criteria for Adverse Events Version 5.0 (NCI CTCAE v. 5.0)

2. Clinical complete response rate of the primary tumor after completion of the neoadjuvant treatment: evaluated by Response Evaluation Criteria in Solid Tumors Version 1.1 (RECIST v1.1)
3. Pathological or clinical complete response rate of the primary tumor after completion of the neoadjuvant treatment: defined as no residual cancer cells in the resected specimen after curative resection
4. Patient's tolerability and completion rate of the neoadjuvant therapy

4. Study Design

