11.2 Planned Statistical methods of analysis

Categorical variables were compared using Pearson's chi-squared test or Fisher's exact test, while continuous variables were compared using the Mann–Whitey U test. Survival curves were generated using the Kaplan–Meier method and compared between the two groups using the log-rank test. The index date of survival analysis was the day the patient started radiotherapy. All statistical analyses were performed using the Statistical Package for Social Sciences (SPSS), version 24 (IBM Corp., New York, NY, USA). Differences were considered statistically significant at a two-sided p-value of < 0.05 .

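### The 30% null rate has no grade while the primary endpoint is grade 3; the named exact test has 75.4% two-sided power at 64, not 80%, and is absent from the listed analyses

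*Protocol*

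**What the plan says.** **Sizing.** Section 11.1, repeated in the synopsis and in 4.2, uses a "one proportion equality test using the exact test to achieving an 80% power at the 5% level of significance". The effect is 15 percentage points "of improvement of acute radiation proctitis (30% to 15"%). No grade, source or sidedness is given. The result is 64 evaluable patients, raised to 72 for 10% loss. The synopsis confirms 72 enrolled and 64 evaluable.

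**Endpoint.** Section 3.2.1 and section 7 give "Grade 3 enteritis/proctitis". The synopsis widens this with "or grade 3 GI AE" and adds a sentence on the cumulative incidence of gastrointestinal symptoms, which carries no grade.

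**Background rates.** Section 2 says "radiation proctitis is a joint adverse event in one-third of patients one week after radiation treatment is complete", without a grade, and that "severe acute toxicity was observed in 4.2% of patients".

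**Analysis.** The synopsis lists "descriptive statistics, Kaplan-Meier method, T-test". Section 11.2 lists Pearson's chi-squared, Fisher's exact, Mann-Whitney and log-rank tests, with survival curves compared between two groups, and says "Differences were considered statistically significant at a two-sided p-value of < 0.05". Section 11.2.5 adds a comparison with other trials and the centre's own retrospective data, and does not say what role it plays.

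**The concern.** In a single-arm trial the fixed null rate does the work of a control group, so it has to be the untreated rate of the endpoint being tested. Here the 30% resembles the background figure for proctitis of any grade, while the endpoint is grade 3.

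- If the untreated grade 3 rate is far below 30%, a test against 30% is passed almost whatever the product does.
- If the null is instead reset to a low grade 3 rate, 64 to 72 patients may be unable to show any reduction.

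Two further problems sit on top of this. The stated power does not belong to the stated test. And the test used for sizing is not among the analyses listed, so a reader cannot tell which analysis decides the primary endpoint.

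**Working it through.** **Inputs.** Null 0.30, alternative 0.15, level 5%, power 80%, exact test, 64 evaluable, 10% loss (all from 11.1). Two-sided is taken from the equality test named in 11.1 and the two-sided criterion in 11.2. The 4.2% is from section 2; the 6%, 10% and 20% rates below are assumptions.

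**1. The plan's own figure.** Two-sided normal approximation:

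n = [(1.96·√(0.30·0.70) + 0.8416·√(0.15·0.85)) / (0.30 − 0.15)]² = [(1.96·√0.21 + 0.8416·√0.1275) / 0.15]² = 63.86, so 64.

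Loss: 64/0.9 = 71.1, so 72. Both stated numbers are reproduced, but by the approximation rather than the exact test. That this is where 64 came from is an inference, since the software output is not in the protocol.

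**2. The named exact test at 64.** With X ~ Bin(64, 0.30):

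- P(X ≤ 11) = 0.0145
- P(X ≤ 12) = 0.0299, which exceeds 0.025

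The test therefore rejects at 11 or fewer. The minimum-likelihood two-sided p-value agrees: 0.028 at 11 and 0.056 at 12. So does the exact 95% interval: 8.9% to 28.7% for 11/64, and 10.1% to 30.5% for 12/64.

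| Reading | Reject at | Power at 15% |
|---|---|---|
| Two-sided exact, n = 64 | ≤ 11 | 75.4% |
| One-sided 5% exact, n = 64 | ≤ 12 | 84.5% |
| Two-sided exact, n = 72 | ≤ 13 | 81.6% |

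Neither exact reading gives 80% at 64.

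**3. Null of 30% when the true untreated rate is lower.** This is the chance that an inert product passes:

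| Assumed true untreated rate | P(≤ 11 of 64) |
|---|---|
| 20% | 0.35 |
| 10% | 0.976 |
| 6% | 0.9996 |
| 4.2% | 0.99999 |

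At 72 patients and a true 10%, P(≤ 13 of 72) = 0.989.

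**4. Null reset to a low rate.**

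- Null 4.2%: P(0 events) = 0.958^64 = 0.064 and 0.958^72 = 0.046, both above 0.025. Even no events at all would not be significant at two-sided 5%.
- Null 10%, n = 64: the test rejects at 1 or fewer. Power for a halving to 5% is P(X ≤ 1 | 0.05) = 0.164.

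**5. Sizing against analysis.** Section 11.1 plans a one-sample test against a fixed rate. As written, Fisher's exact, Mann-Whitney, log-rank and t-tests compare groups, and the other listed methods are descriptive or correlational. None is named as a one-sample exact binomial test.

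**The case against.** **Power.** Section 11.1 gives no sidedness, and a one-sided exact test has 84.5%, above target. Exact power is also saw-toothed (80.4% at 61, 75.4% at 64), and analysing all 72 would restore 81.6%. This is fair as to size: the shortfall is 4.6 points at one sample size and depends on the two-sided reading. But the protocol's wording supports that reading, 64 is the evaluable number it plans for, and no exact reading yields 80% there.

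**Rates.** The 4.2% is not specific to proctitis, the 6% and 10% have no source in the protocol, and the untreated rate of the wider synopsis endpoint is unknown. At a true 20% an inert product passes with probability only 0.35. This also stands: near-automatic success needs a rate of roughly 10% or less. It does not supply what is missing, a grade-matched rate to justify 30%.

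**Analysis.** Pearson's chi-squared can be run as a one-sample test against a fixed proportion. At 64 it would reject at 12 or fewer (p = 0.0495) with 84.5% power and a true size of about 5.6%. But 11.2 presents it for comparisons, it is not exact, and it would exceed 5%. Much analysis detail may properly wait for the statistical analysis plan. What remains is narrower: 11.1, 11.2 and 11.2.5 describe different analyses within one document.

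**Conclusion.** The point holds. The main defect is that the null rate has no grade while the endpoint is grade 3, and the protocol offers no grade 3 rate near 30%. How far this undermines the result depends on an untreated rate the protocol does not give: an inert product passes with probability 0.976 at an assumed 10%, and 0.35 at an assumed 20%.

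If 30% to 15% does apply to the tested endpoint, power is modestly overstated: 75.4% rather than 80% at 64 evaluable patients, on the two-sided reading. In either case the listed analyses do not include the test on which the trial was sized.

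**What to change.** 1. Make the endpoint and the null rate refer to the same definition and grade in the synopsis, 3.2.1, 4.2, 7 and 11.1, and cite the source of the rate.
2. If 30% is not the untreated rate of that endpoint, restate the null and recompute power and sample size.
3. If 30% to 15% stands, state that the test is two-sided, give the rejection rule (11 or fewer of 64), check 64 against the software output, and restate power as about 75% at 64 evaluable, or about 82% only if all 72 are analysed.
4. In 11.2, name the one-sample exact binomial test against that null, with an exact 95% confidence interval, as the primary analysis. Describe the comparison in 11.2.5 as supportive, and say which two groups 11.2 means.

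**Cost.** If 30% is confirmed, this is wording only and no patients are added, but the sponsor accepts about 75% power. Keeping two-sided exact power above 80% from that size onward would need 70 evaluable patients, or 70/0.9 = 77.8, so 78 enrolled. If 30% is not confirmed, the calculation must be redone and the sample size may change.

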11.2 Planned Statistical methods of analysis

Categorical variables were compared using Pearson's chi-squared test or Fisher's exact test, while continuous variables were compared using the Mann–Whitey U test. Survival curves were generated using the Kaplan–Meier method and compared between the two groups using the log-rank test. The index date of survival analysis was the day the patient started radiotherapy. All statistical analyses were performed using the Statistical Package for Social Sciences (SPSS), version 24 (IBM Corp., New York, NY, USA). Differences were considered statistically significant at a two-sided p-value of < 0.05 .

11.2.1 Efficacy analysis

Adverse events are assessed by the clinician on each cycle of admission, and additional record of adverse events (CTCAE version 5) by our research nurse on every 3 cycles of chemotherapy.

Clinical complete remission is evaluated on each colonoscopy examination after the neoadjuvant chemotherapy and radiation therapy completed according to Response Evaluation Criteria in Solid Tumors Version 1.1 (RECIST v1.1). In addition, the pathologist evaluates pathological complete response and tumor regression grade after curative resection.

11.2.2 Safety analysis

The adverse events and complete blood count is evaluated on each admission for chemotherapy. Serum creatinine, electrolyte, AST, ALT, total and direct bilirubin is examined on each 3 cycle of chemotherapy. Adverse events are assessed by the clinician on each cycle of admission, and additional evaluation of adverse events (CTCAE version 5) by our research nurse on every 3 cycles of chemotherapy, which is the standard follow-up scheduled of the chemotherapy.

